1.1.2 Hypotheses and Objectives

Hypotheses:

Social support in the abortion procedure room will decrease perceived pain and anxiety levels and increase satisfaction for the patient.

- 1. Social support in the procedure room influenced the patient's health outcomes in the following areas:
 - 1. Decreased pain
 - 2. Decreased anxiety
 - 3. Increased patient satisfaction
- 2. The social support person will report that they were able to give effective support to the patient.
- 3. The physician and the nurse will find the support person effective in supporting the patient.

Null Hypothesis:

- 1. Social support in the abortion procedure room will not change patient levels of perceived pain, anxiety, or satisfaction.
- 2. The social support person will report they did not give adequate support.
- 3. The health care provider and the surgical assistant will not find the support person effective

in supporting the patient.

Objectives

Primary Aims:

- To assess a change in expected pain level from baseline, immediately after the procedure, and again ten minutes after arrival to the recovery room as determined by a 100mm visual analog scale (VAS) for patients with in-room social support during the procedure as compared to those who do not.
- To assess pre- and post-procedure state anxiety levels as determined by the 20-question State-Trait Anxiety Inventory (STAI) for patients with in-room social support as compared to patients without in-room social support.

Secondary Aims:

- To measure acceptability and effectiveness of having social support in the procedure room as reported by the surgical assistant and healthcare providers as determined by a post-procedure questionnaire.
- To evaluate if support was effectively given to the patient as reported by the support person as determined by a post-procedure questionnaire.

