1.3.2 Sample Size

A total of 400 subjects will be enrolled in this study; 200 participants will enroll in the control arm and 200 will enroll in the intervention arm. Within these two arms, 100 subjects will be "patients" and "support persons." "Patients" are defined as people who will receive an in-clinic abortion on the day of their participation. "Support persons" are the individuals whom the patient chooses to accompany them during the in-clinic abortion procedure. Support persons will only actually accompany patients in the in-clinic procedure room if they are randomized to the

intervention arm of this study. Health care providers will also be invited to participate in this research study—and enrollment numbers will depend upon the amount of unduplicated staff who will perform or assist with the D&C procedure on days when enrollment will occur. "Health care providers" include the physician performing the abortion and nurses assisting the physician within the abortion procedure room.

Prior studies indicate a 20mm difference in VAS is clinically significant and that the common standard deviation for VAS scores is 23 mm [8]. Based on these assumptions, a sample size of 28 with 14 women in each arm will have 90% power to detect at least a 20mm difference between the change in pain score from baseline, to during the procedure, to after the procedure between the two groups, using a Student's t-test evaluated at the 2-sided 0.05 significance level.

We have chosen a larger sample size to also provide a representative sample of our patient population for our secondary aims of patient and support person satisfaction as well as nurse and physician satisfaction. This sample size was calculated based on the total number of in-clinic abortion patients seen in the Tampa Health Center in 2015 with a Confidence Level of 95% and a Confidence interval of 10.

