1.3.11 Data Analysis

Analysis will be performed using Qualtrics statistical software. Analyses will be performed on all control and experimental group data. The control group is defined as the standard care without presence of support person, whereas the intervention group is all those receiving standard care with the presence of a support person in the procedure room. Demographic, behavioral, and clinical characteristics will be compared between the two arms using frequency tests, Student's ttest, chi-squared tests, and two-way ANOVA, where appropriate. The change in pain score, as assessed by VAS, from baseline to recovery room will be compared within each group using paired Student's t-test if the data are normally distributed or Wilcoxon signed-rank test if the data do not follow a Gaussian distribution. Similarly, the difference in the change in VAS scores between the

study arms will be compared using Student's t- or Mann-Whitney U tests, where appropriate. Questionnaire answers will be compared between both arms of the study using chi-squared statistical analysis. Statistical analysis will be performed by both the Principal Investigator and statistician.

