4. RESEARCH INSTRUMENTS/QUESTIONNAIRES

4.1 SUBJECT DEMOGRAPHIC QUESTIONNAIRE – INTERVENTION ARM

Please fill in the information below, if applicable: Age: _____ Gestational age (How many weeks pregnant are you?) Number of children: _____ Number of previous abortions: Religion: Please circle your answers below: Ethnicity: Hispanic Non-Hispanic Race: American Indian or Alaska Native Asian Black or African American Native Hawaiian or other Pacific Islander White Two or more races **Marital Status**: Single Married Divorced Widowed Separated Are you using your insurance for the procedure? No Yes Are you receiving sedation for the procedure? Yes No What is your relation to the patient/support person?

${\bf 4.1~SUBJECT~DEMOGRAPHIC~QUESTIONNAIRE-CONTROL~ARM}$

Please fill in the information below, if applicable:

Age:						
Gestational	age (H	ow many we	eks pregnant are	e you?)		
Number of	childre	n:				
Number of j	previou	ıs abortions:				
Religion:						
	your a	nswers below				
	Non-	Hispanic				
Race:	Ame	rican Indian o	or Alaska Native			
	Asia	n				
	Black	k or African A	American			
	Nativ	ve Hawaiian o	or other Pacific Isl	lander		
	Whit	e				
	Two	or more race	S			
Marital Sta	tus:	Single	Married	Divorced	Widowed	Separated
Are you usi	ng youi	r insurance f	or the procedure	?	Yes	No
Are you rec	eiving s	sedation for	the procedure?	Yes	No	
What is you	ır relati	ion to the pa	tient/support per	rson?		

4.2 POST-PROCEDURE QUESTIONNAIRE FOR PATIENT - INTERVENTION ARM Please circle your answers below:

1.	I would rate my overall satisfaction with the procedure as: Very satisfied
	Somewhat satisfied
	Neutral
	Somewhat dissatisfied
	Very dissatisfied
2.	The amount of discomfort I experienced during the procedure was acceptable. Definitely yes
	Probably yes
	Neutral
	Probably not
	Definitely not
3.	I feel that the amount of support I received from my support person in the procedure room helped decrease my pain. Definitely yes
	Probably yes
	Neutral
	Probably not
	Definitely not
4.	I feel that I received all the support I needed from my support person in the procedure room. Definitely yes
	Probably yes
	Neutral
	Probably not
	Definitely not
La	st updated: 4/10/2017

5. The presence of my support person in the procedure room made me feel uncomfortable.
Definitely yes
Probably yes
Neutral
Probably not
Definitely not
6. If you were uncomfortable in the procedure room, were you uncomfortable due to any of the following: (Circle all applicable options)

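### Ordered five-point patient items worded identically in both arms are compared by chi-squared, which ignores their order; an ordered test would be more powerful against the hypothesised shift and costs nothing to name

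*Protocol*

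**What the plan says.** Section 1.1.2 lists "Increased patient satisfaction" as one of three patient outcomes under hypothesis 1, beside decreased pain and decreased anxiety.

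The patient questionnaires in sections 4.2 (intervention) and 4.3 (control) both open with the same item, "I would rate my overall satisfaction with the procedure as: Very satisfied", followed by four further answers running down to very dissatisfied. Item 2, on whether the discomfort was acceptable, is also worded identically in the two arms and runs over five ordered answers from definitely yes to definitely not.

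Section 1.3.11 fixes the comparison: "Questionnaire answers will be compared between both arms of the study using chi-squared statistical analysis". It names no ordered test, trend version or collapsing of categories for these answers. In the same section, the between-arm comparison of change in VAS is allowed a Student's t-test or a Mann-Whitney U test as appropriate, so a rank test is already in the plan, but for pain only.

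On size, section 1.3.2 says "200 participants will enroll in the control arm and 200 will enroll in the intervention arm", and continues: "Within these two arms, 100 subjects will be". I read this as 100 patients and 100 support persons in each arm. The same section treats patient satisfaction as a secondary aim and justifies the larger sample by precision (95% confidence, interval of 10). It states no power for satisfaction.

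**The concern.** The Pearson statistic on a 2x5 table is unchanged if the five columns are put in any other order. It asks whether the arms differ in any way at all and spreads the evidence over 4 degrees of freedom. Hypothesis 1 is narrower: answers should move towards the satisfied end. A test that uses the order concentrates on that one direction.

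Two things are at stake. A real and consistent gain in satisfaction is more likely to be missed. And the chi-squared test yields a p-value with no estimate of how much better the answers are. Section 1.3.11 plans no other comparison of satisfaction, so nothing elsewhere makes up for this.

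**Working it through.** **The plan's own figure.** There is none for satisfaction. The only power statement concerns pain: "a sample size of 28 with 14 women in each arm will have 90% power to detect at least a 20mm difference", with "the common standard deviation for VAS scores is 23 mm". The usual two-sample formula gives n per arm = 2 x (1.960 + 1.282)² x 23² / 20² = 27.8, that is 28 per arm rather than 28 in total; 14 per arm gives about 63% power. This is a separate matter, and the planned 100 patients per arm exceed it. It does not bear on the choice of test for questionnaire items.

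**Inputs.**
- From the protocol: five ordered categories; 100 patients per arm (section 1.3.2, as read above).
- Borrowed: two-sided 0.05, which section 1.3.2 states for pain only ("using a Student's t-test evaluated at the 2-sided 0.05 significance level").
- Assumed: the control-arm answer distribution; a proportional-odds shift of a given odds ratio (OR) for a better answer; independent patients; no missing answers.

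**Benchmark.** An efficient ordered test has 80% power when its noncentrality is (1.960 + 0.842)² = 7.85 on 1 degree of freedom. The same noncentrality on 4 degrees of freedom (critical value 9.49) gives 59.5%. The loss is 80 - 59.5 = 20.5 points. Repeating this at other levels:

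| Ordered test (1 df) | Chi-squared (4 df) | Loss, points |
|---|---|---|
| 30% | 17.6% | 12 |
| 50% | 30.8% | 19 |
| 70% | 48.2% | 22 |
| 80% | 59.5% | 20.5 |
| 90% | 74.0% | 16 |
| 95% | 83.7% | 11 |

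**One case by hand.** Take control answers of 40/30/15/10/5% and OR 2. For the top answer the odds go from 0.40/0.60 = 0.667 to 1.333, so 40% becomes 1.333/2.333 = 57.1%. Doing the same at each cut gives 57.1/25.2/9.5/5.5/2.6%. With equal arms the Pearson statistic is the sum over categories of (difference in counts)² / (total count). At the expected counts this is 3.03 + 0.42 + 1.22 + 1.28 + 0.78 = 6.72. On 4 degrees of freedom that noncentrality gives 52% power. If an ordered test captures essentially all of it on 1 degree of freedom, the power is about Φ(√6.72 - 1.96) = Φ(0.63) = 74%.

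**Simulation.** 20,000 trials per setting, 100 patients per arm, Pearson chi-squared (empty columns dropped) against tie-corrected Mann-Whitney:

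| Control answers, % | OR 1.5 | OR 2 | OR 3 |
|---|---|---|---|
| 40/30/15/10/5 | 19 v 34 | 51 v 74 | 91 v 98 |
| 60/25/8/5/2 | 15 v 29 | 41 v 64 | 80 v 94 |
| 80/14/3/2/1 | 9 v 19 | 22 v 42 | 48 v 73 |

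The first row agrees with the hand calculation. Three other control distributions at OR 2 gave 47% v 70% (50/28/12/6/4), 41% v 64% (60/25/8/4/3) and 55% v 76% (30/30/20/12/8). In those three the loss was about 13 to 16 points at OR 1.5 and 6 to 14 at OR 3. When satisfaction is already very high (80% at the top), the gap is 10 points at OR 1.5 and peaks later, at 25 points for OR 3.

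**Where the loss shrinks or reverses.**
- *Collapsing.* Applying chi-squared to very satisfied against the rest loses only 0 to 4 points in the three tabulated distributions. With answers spread evenly over the five categories it does not help: 57% against 79% at OR 2.
- *Shifts confined to part of the scale.* With 40/30/15/10/5% moving to 55/15/15/10/5%, chi-squared had 57% power and Mann-Whitney 28%. Two other such patterns gave 56% v 20% and 62% v 47%.
- *No effect.* At OR 1 the chi-squared test rejected in 3.0% (most skewed setting) to 5.1% of trials, so it is not anti-conservative.

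**The case against.** The best defence is that chi-squared is a valid test here and that the rest is a preference about efficiency. Several parts of it stand.

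- A reader might infer that the trial gives up more than 20 points of power. The documents do not support that as a property of this trial. They give no effect size and no expected answers for satisfaction, and the figure depends on both. Proportional odds is also the setting that favours the ordered test.
- Section 1.3.11 says only chi-squared. It neither specifies nor rules out collapsing or a trend version, and in skewed data a two-category split would lose little. But no such version is stated, and the plain reading for a five-category answer is the 2x5 table.
- A reader might infer that few dissatisfied answers make the chi-squared approximation unreliable. Expected counts below 5 are likely in skewed settings, but the error rate at OR 1 did not exceed 5% beyond simulation noise, so no such claim is made.
- A reader might extend the point to the preference item (intervention item 8, control item 4). These are not worded alike: the intervention version asks about being accompanied again, after actual accompaniment. It does not belong in a like-for-like comparison.
- Direction can be read from the proportions in the table, so chi-squared does not hide it. What is missing is a test aimed at that direction and an estimate of its size.
- Section 1.3.2 treats satisfaction as secondary and sizes it for precision, so no promised power is lost.

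What this does not answer is why the plan should discard the ordering for an outcome whose hypothesis depends on it, when it already allows a rank test for VAS change.

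**Conclusion.** The point holds as a low-cost improvement, not as an invalid analysis. For patient items 1 and 2, the test fixed in section 1.3.11 ignores the order, gives no effect estimate, and is less powerful against a consistent shift towards satisfaction. The loss is about 20 points in the middle range, where an ordered test would have roughly 50% to 80% power. In three of the assumed control distributions it is about 13 to 16 points at OR 1.5 and 6 to 14 at OR 3. Over all settings tried at OR 1.5 to 3 it ran from about 4 to 25 points.

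These figures rest on assumed control distributions, proportional odds, 100 independent patients per arm, two-sided 0.05 and an uncollapsed table. Section 1.3.1 randomises procedure days, not patients. Correlation within days would lower the power of both tests and could change the gap; the figures do not cover that.

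**What to change.** In section 1.3.11, replace the blanket chi-squared sentence for the ordered patient items that both arms share. Compare items 1 and 2 between arms with a Wilcoxon-Mann-Whitney test or a proportional-odds model, and report the common odds ratio with its 95% confidence interval, allowing for procedure day as the randomised unit in the same way as for the other outcomes. Keep chi-squared for unordered items, such as reasons for discomfort and type of concern. Leave the preference item out of this like-for-like comparison.

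Naming the test takes one sentence and needs no extra data, patients or visits. The handling of procedure day needs its own specification, which the other outcomes need in any case. The downside is small: an ordered method relies on a roughly consistent shift across the scale and can do worse than chi-squared if the effect sits in only part of it. Tabulating all five answers by arm would show whether that happened.

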1.3.12 Study Limitations

Potential weaknesses in the internal validity of this study are addressed through the study design of a randomized controlled trial. Through randomization, the two study groups should theoretically have similar subject characteristics. One potential weakness is that blinding cannot occur. Also, patients in the control group may be dissatisfied and more anxious at baseline due to knowing that they may not have their desired support person in the procedure room.

One limitation in this study is the potential variation among different providers during inclinic abortion; however, all providers will follow the same set standards for the in-clinic abortion procedures. This, combined with the fact that there are only a small number of rotating providers should decrease this potential limitation.

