1.3 Design and methodology

1.3.1 Research design and General Methodological Approach

This study will be designed as a randomized, controlled trial to compare pain and anxiety levels before, during, and after in-clinic abortion in patients with and without a support person in the abortion procedure room. Each procedure day will be randomized into "support person day" ("intervention group") or "non-support person day" ("control group"). This randomization process was chosen as the most effective way to randomize without compromising patient care and study validity. Limitations to the physical space of the health center prevent patient randomization because there is no way to avoid patients knowing which arm of the study they are in: the intervention arm or the control arm.

Randomization will occur at the beginning of each procedure day by a research assistant who will pull from an opaque envelope that contains ten slips of paper, five will be marked with 'A' and the other five marked with 'B'. The half marked 'A' will indicate the procedure day will be assigned as an "intervention" day, and the other half marked 'B' will indicate the day will be assigned as a "control" day. After all ten slips of paper are pulled and ten of the procedure days have been randomized, the research assistant will replace the ten slips of paper and begin the same randomization process until the designated number of participants have been enrolled. The research assistant will initiate enrollment of patients in the study after they have consented for the abortion procedure.

All patients who present at PPSWCF's Tampa Health Center for a dilation and curettage (D&C), whether for elective pregnancy termination or management of early pregnancy complications and who are proficient enough in English to consent and understand the study procedures are eligible for participation and enrollment. Support people will be eligible for participation and enrollment if they are 18 years of age or older, are privately selected by the patient to be their support person, and who are proficient enough in English to consent and understand the study procedures. Support people for minors will be privately selected by the patient in conjunction with their parent/guardian consent.

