1.3.8.1 Patient Procedure and Questionnaires

- 1) After patients have consented for the D&C procedure and the study, they will complete a paper questionnaire. This questionnaire will contain demographic information and type of sedation chosen. Additionally, subjects will record their baseline level of expected pain prior to the start of the procedure. The subject will also complete the State Trait Anxiety Inventory (STAI) after the informed consent process and before the procedure starts.
- 2) On randomized intervention days, the patient will be accompanied in the procedure room by a support person.
- 3) The study physician will enter the room and perform the abortion procedure in the usual manner. The abortion procedure will remain the same on intervention days as on control days. Immediately after the procedure, the patient will complete the second 100mm VAS. Any deviations from this protocol will be recorded.
- 4) Once the patient is in the post-abortion recovery room, the patient will complete the STAI again, a post-procedure questionnaire, and the final pain level on the 100mm VAS will be recorded at least ten minutes after arrival to the recovery room. After all questionnaires have been completed and returned to research staff, the subject will be given their reimbursement gift card for participation.
- 5) The patient's complete questionnaires will be manually entered in the Qualtrics data management software which will only be managed by designated research staff. Study documents, including surveys, will be stored in a locked filing cabinet and will be accessed by research personnel only.

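### The between-arm pain comparison is change from an expected-pain score taken after the day's arm is drawn, so an effect of knowing the arm on that score would pass straight into the result

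*Protocol*

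**What the plan says.** **Order of events.** Protocol 1.3.1: "Randomization will occur at the beginning of each procedure day by a research assistant", and "The research assistant will initiate enrollment of patients in the study after they have consented for the abortion procedure". The same section explains whole-day allocation by the clinic's space: "there is no way to avoid patients knowing which arm of the study they are in".

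**The baseline.** Under 1.3.8.1, after study consent, "subjects will record their baseline level of expected pain prior to the start of the procedure". The form in 4.4 asks for a forecast of pain during the procedure, not for current pain. VAS 2 and VAS 3 ask for current pain at the end of the procedure and in the recovery room.

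**What rests on it.** The first primary aim (1.1.2) is change from expected pain, by arm. The power statement (1.3.2) is for a "difference between the change in pain score from baseline, to during the procedure, to after the procedure between the two groups". Section 1.3.11 says "The change in pain score, as assessed by VAS, from baseline to recovery room will be compared within each group" and then tests "the difference in the change in VAS scores between the" arms by Student's t or Mann-Whitney U.

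**The concession.** Section 1.3.12: "patients in the control group may be dissatisfied and more anxious at baseline due to knowing that they may not have" the support person they wanted. It is listed as a limitation only.

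**The concern.** A change score is safe in a randomised comparison when the baseline cannot be affected by allocation. Here VAS 1 comes after allocation for every patient. It is also a forecast of procedure pain, in a trial whose hypothesis is that a companion in the room lowers that pain. A patient who knows whether she will be accompanied could reasonably forecast differently.

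If control patients forecast more pain because they know their arm, their scores start higher and appear to fall further, and a real benefit of the support person is understated. If the shift runs the other way, benefit is overstated. More patients would not remove the error. The project summary says the result could change standard procedure-room practice, so an error in either direction matters.

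**Working it through.** **Inputs from the protocol.** Target difference 20 mm, SD 23 mm (given for VAS scores, not for change), two-sided 0.05, 90% power (1.3.2). There are 200 participants per arm enrolled in patient and support-person pairs, read as 100 patients per arm.

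**Assumed inputs.** s = control minus intervention difference in VAS 1 caused by knowing the arm, shown at 0, 2 and 5 mm. r = correlation of VAS 1 with post-procedure VAS, 0 to 0.7. SD 23 mm at both times.

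**The plan's own figure.** n per arm = 2 × [23 × (1.960 + 1.282) / 20]² = 27.8, so 28 per arm (29 by exact t). The protocol gives 28 in total, 14 per arm, which yields about 60% power by exact t. This is a separate matter. The planned 100 per arm exceeds either number, and the calculations below use 100.

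**Bias of the change score.** Let B be the effect of allocation on post-procedure pain (control minus intervention).

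Estimated benefit = (post_C − post_I) − (VAS1_C − VAS1_I) = B − s.

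This holds for any SD or r. At s = 2 mm, 2/20 = 10% of the target is lost; at s = 5 mm, 5/20 = 25%.

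**What that could do to the test (illustration).** SD of change = 23 × √(2(1 − r)); SE = SD × √(2/100); noncentral t, 198 df. With B = 0, the chance of a significant result against the support person is:

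| r | SD of change (mm) | SE (mm) | s = 0 | s = 2 mm | s = 5 mm |
|---|---|---|---|---|---|
| 0 | 32.5 | 4.60 | 0.025 | 0.063 | 0.190 |
| 0.3 | 27.2 | 3.85 | 0.025 | 0.075 | 0.252 |
| 0.5 | 23.0 | 3.25 | 0.025 | 0.089 | 0.334 |
| 0.7 | 17.8 | 2.52 | 0.025 | 0.121 | 0.506 |

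Allowing for day clustering (assumed: 10 patients per day, 20 days, ICC 0.05; design effect 1 + 9 × 0.05 = 1.45; 18 df), the ranges over r are 0.053 to 0.091 at s = 2 mm and 0.135 to 0.345 at s = 5 mm. With a true benefit of 10 mm, r = 0.5 and no clustering, power falls from 86% at s = 0 to 33% at s = 5 mm.

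**Adjusting for VAS 1 instead.** With equal SDs the bias left is r × s. For s = 5 mm that is 1.5 mm at r = 0.3 and 3.5 mm at r = 0.7, so adjustment removes only part of it.

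**Post-procedure VAS compared directly.** No VAS 1 term enters, so s drops out. SE = 23 × √(2/100) = 3.25 mm. Power for 20 mm is above 99.9%, or 99.8% with the assumed clustering. The smallest difference with 90% power, clustering ignored, is 10.6 mm, against 15.0, 12.5, 10.6 and 8.2 mm for the change score at r = 0, 0.3, 0.5 and 0.7.

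**The case against.** **Disclosure before VAS 1 is not documented.** The remark in 1.3.1 explains why individual randomisation was rejected; it does not say when a patient learns her arm. The conditional wording in 1.3.12 can be read as uncertainty shared by both arms, in which case s = 0. This stands and limits the point to a risk. The form headings do not settle it: the VAS form has no arm label, and the labels on the demographic form may only be appendix headings.

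**The concession is about anxiety and dissatisfaction.** Correct. A reader might infer that the protocol admits a biased pain baseline. It does not; the step from anxiety to expected pain is an inference.

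**Enrolment was not set by the change score.** Also correct. Only the 28-patient calculation uses change. Actual enrolment follows a separate precision rule (95% confidence, interval of 10), so it would be too strong to say that the trial's size rests on VAS 1.

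**The alternative may carry its own bias.** Suppose disappointment raises control scores throughout and a fraction c of s persists after the procedure. Measured against the effect of the companion's presence alone, the change score is biased by −(1 − c)s and the post-procedure comparison by +cs. At s = 5 mm, SD 23 mm and 100 per arm, a false result in favour of the support person then occurs 12% of the time at c = 0.5 and 33% at c = 1. This addresses a different question. In an unblinded trial, disappointment carried into post-procedure pain is part of the effect of allocation, which is what a comparison by arm estimates. It stands as a caution for interpretation.

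**Enrolment follows the draw.** Knowledge of the arm could affect who consents, and a limited number of days may differ by chance. A post-only comparison corrects for neither; a change score does so in part. This stands, and it is why the between-arm change score should be kept as a supporting analysis.

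**Conclusion.** The point holds as a design weakness that should be corrected, with medium confidence. The documents establish that VAS 1 follows the draw, that knowledge of the arm is not preventable, and that the aim, the power statement and the between-arm test use change from VAS 1. They do not establish that a bias exists or how large it is. If s is not zero, the estimate of the effect of allocation is off by s mm, apart from any real effect on post-procedure pain. The rejection rates and power losses also rest on assumed r and, where clustering is included, on an assumed ICC, day count and day size.

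Two stronger readings should be avoided: that patients are shown to know their arm when they mark VAS 1, and that the planned anxiety analysis has the same error. The pre-procedure STAI is also taken after the draw, but 1.3.11 states no STAI change score, so the analysis finding is confined to VAS.

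**What to change.** 1. Make the primary between-arm pain comparison on post-procedure VAS, immediately after the procedure and in recovery, by allocated arm. Reword 1.1.2, 1.3.2 and 1.3.11 to match. Keep the between-arm change from VAS 1 as a secondary or sensitivity analysis.
2. Use one baseline form without an arm label. Where existing staff can do so, have VAS 1 and the pre-procedure STAI completed before the pair is told the arm, and state in the protocol when disclosure occurs. With whole-day allocation this may protect mainly the first pair of each day, so step 1 carries most of the weight.

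**Cost.** Three sections reworded and one form merged, with no added patients, visits or staff. Power for 20 mm stays above 99% at SD 23 mm. Precision is lost against the change score only if r exceeds 0.5: at r = 0.7 the difference detectable with 90% power is 10.6 mm against 8.2 mm, a loss of 2.4 mm (100 per arm, clustering ignored). The new comparison neither removes unblinded reporting of pain nor corrects for arm-dependent enrolment after the draw.
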